Patients with previous diagnosis of histoplasmosis will not be considered for this study. We will also exclude pregnant or lactating woman, patients with renal failure (serum creatinine and urea >1.5 times the upper limit of normality), abnormal aminotransferases (up to >3 times the upper limit of normality), and patients with a previous serious reaction to a polyene antifungal drug. Patients who received more than one dose of a polyene antifungal drug in the last 48 hours will be excluded, as well as patients who refuse content to participate in the study. Patients diagnosed with histoplasmosis affecting the central nervous system will not be allowed to participate in the study. In addition, patients who are expected to die within 48 hours of enrolment will also be excluded, based on the judgment made by the attending physician. Patients diagnosed with tuberculosis will be excluded; as well those receiving drugs that cause significant drug-drug interaction (relative or absolute) with itraconazole.

Study settings

Six medical centers in Brazil, will recruit patients for this study: Santa Casa de Misericórdia de Porto Alegre, Hospital de Clínicas de Porto Alegre, Hospital Nossa Senhora da Conceição, Hospital de Doenças Tropicais, Hospital São Jose de Doenças Infecciosas, and Hospital Giselda Trigueiro.

Intervention

AIDS patients with DH will be randomized to one of three study arms: (i) single IV dose of L-AmB at 10 mg/kg; (ii) single IV dose of 10 mg/kg of L-AmB on day 1, followed by 5 mg/kg of L-AmB on day 3; and (iii) L-AmB at 3 mg/kg IV for 2 weeks. Induction therapy will be followed in all patients by oral therapy with itraconazole capsules at 400 mg/daily for a year.

Drug reconstitution and administration

L-AmB (AmBisome; Gilead Sciences, San Dimas, California, USA), a lyophilized liposomal preparation of amphotericin B, will be reconstituted according to the manufacturer's instruction and given intravenously at fixed doses, according to the randomization arm. L-AmB concentration should be of 0.2 mg/ml in 5% dextrose, and the drug should be infused over 2 hours, preferably in a central line. Patients will be monitored for the occurrence of infusion-related toxicity during and after drug infusion.

Primary endpoint

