Clinical and mycological successes will be the primary outcomes for this study. A successful clinical response to induction therapy will be defined according to, as a maximum daily temperature $<37.8^{\circ}\text{C}$ for 72 hours; no increase in severity of clinical signs, symptoms, or laboratory abnormalities attributable to histoplasmosis; and the resolution of at least one of the signs or symptoms of histoplasmosis that qualified the patient for study enrollment [7].

Primary study outcome will be determined at day 14 of the study.

Secondary endpoints

Overall mortality and investigator-attributable mortality due to histoplasmosis will be determined at day 14 of study. Overall Survival (OS) will also be determined at 12, 24, and 48 weeks of study. OS will be considered as the time from randomization until death from any cause.

Secondary endpoint will also include need for an additional antifungal course with L-AmB, during 24 weeks of follow up.

Median percentage of change in renal and hepatic function at 14 days will be compared with baseline values.

Frequency of infusion-related toxicity with L-AmB will be recorded.

Clearance of blood cultures will not be used as a criterion for mycological response in this study, due to the limited sensitivity of blood culture in histoplasmosis [19]. Fungal clearance will also not be used as a criterion for mycological response. Differently from cryptococcosis, in which fungal burden is easily obtained and quantified in cerebrospinal fluid samples,

in histoplasmosis commonly a single positive sample is obtained along patient investigation (e.g., microscopy, culture, and/or histopathology).

Non-culture laboratory markers have proved to be useful adjuncts in monitoring the response to systemic histoplasmosis [20, 21]. In this study, we will evaluate the effect of a decrease of at least 50% in *Histoplasma* urinary antigen concentrations [19] along the first 2 weeks of therapy as a secondary endpoint, and the association of such reductions with clinical response to antifungal therapy.

Rescue therapy

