The study protocol will allow patients to receive additional courses of L-AmB (at 3 mg/kg daily) in case the attendant physician suspect of absence of response with the induction regimen. This will apply for failing patients receiving a single 10 mg/kg of L-AmB; or 10 mg/kg on day 1, followed by 5 mg/kg on day 3. In these cases, L-AmB should be given up to a maximum period of 2 weeks. The estimated frequency of L-AmB as rescue therapy will be based on the frequency of failure with L-AmB at 3 mg/kg in patients with DH and AIDS (i.e., 12%) [7]. Considering that 66 patients will be evaluated in arms (i) and (ii) of the study (high-doses of L-AmB), in a pessimistic scenario we aim to provide 8 additional treatments with L-AmB.

Time for initiating ART

Physicians will be instructed to initiate ART as soon as possible in AIDS patients with DH, since immune reconstitution syndrome is uncommon in patients with DH [22]. In Brazil, initial ART consists of dolutegravir, lamivudine, and tenofovir. History of previous antifungal use and known resistance patterns will also be considered in the decisions about ART.

Statistical analyses

Descriptive statistics will be used to summarize the data. Mean, standard deviation, median, interquartile range and minimum and maximum will be described for continuous variables. Categorical variables will be summarized by absolute and relative frequencies. Kaplan-Meier method will be used in order to describe OS. Despite the non-comparative status of the

trial, exploratory comparisons will be performed across subgroups. Continuous variables will be compared using two sample t-test, paired sample t-test, Mann-Whitney test, Wilcoxon signed-rank test, one-way ANOVA or Kruskal-Wallis test, as appropriate and necessary. Categorical variables will be compared with Fisher exact test or chi-square test, as appropriate. All p-values will be two-sided.

We expect that the three arms will have the same clinical response. For each arm, when the sample size is 29, a two-sided 90% confidence interval will extend 10% from the observed proportion for an expected proportion of response equal to 88% [as extracted from the Johnson trial]. Considering a dropout of 10%, the sample size per arm will be 33. The total sample size for the study will be 99 patients. Data analysis will be performed using SPSS software.

Ethical aspects

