Conduction of this study is conditioned to ethical approval by local IRBs. Since this trial will not aim to modify any regulatory aspect related to L-AmB in Brazil, ANVISA (Brazilian Health Regulatory Agency) will not be consulted. The study will also be registered at clinicaltrials.gov.

Study activities

Clinical evaluations will take place at baseline, day 3, day 7, and day 14 (End of Study Visit). End of follow up will occur at week 48, and mortality will be determined at weeks 12, 24, and 48.

The study will recommend careful attention to hydration status, and close monitoring of renal function, hepatic function, and electrolytes. Unless clinically advisable, physicians are requested to give one liter of saline 0.9% solution intravenously before L-AmB infusion. Patients should also be on prophylaxis with daily trimethoprim-sulfamethoxazole.

Table 1 shows the procedures predicted for this study. Clinical and laboratory adverse events will be graded using the NIH DAIDS Toxicity Table [23]. Itraconazole therapeutic drug monitoring will be offered to sites at day 7 and day 14 of study. The attending physicians will use this information according to their personal judgment.

Table 1. Study activities.

	Baseline	Day 3	Day 7	Day 14	Week 12	Week 24	Week 48
Informed Consent	X						
History	X						
Physical Exam	X		X	X			
Maximum Temp	X	X	X	X			
Glasgow coma scale	X		X	X			
Chemistry (including magnesium) and blood counts	X		X	X			
HIV documentation	X						
CD4 count determination							
Pregnancy Test	X						
Chest X-ray	X			X			
Study Drug accountability	X						
Concomitant medications	X	X	X	X			
Adverse Events		X	X	X			
Survival determination				X	X	X	X
Molecular test for TB	X						
Urine for Histo antigen test	X		X	X			
Histoplasma PCR (as needed)	X						
Fungal culture (as needed)	X						
Microscopy (as needed)	X						
Histopathology (as needed)	X						
Itraconazole TDM			X	X			
Lysis centrifugation (if available)	X						
Study responde determination				X			
Need for additioal course of L-AmB				X	X		

Study Plan Schedule Strategy

Table 2 shows the predicted timeline for this study.

Table 2. Study plan.

References

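### Infusion-related toxicity has no stated unit, so a per-patient comparison of arms with 1, 2 and about 14 infusions cannot separate dose level from number of infusions

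*Combined protocol and SAP*

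**What the plan says.** Under Secondary endpoints, the whole specification is "Frequency of infusion-related toxicity with L-AmB will be recorded". It does not say whether the count is of patients, infusions or events, and it sets no definition, grade threshold or time window.

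Under Intervention, arm (i) has one infusion, at 10 mg/kg. Arm (ii) has two: the first at 10 mg/kg and the second, given on day 3, at 5 mg/kg. The third arm is described as "L-AmB at 3 mg/kg IV for 2 weeks". Rescue therapy allows patients failing in arms (i) and (ii) up to two weeks of further L-AmB at 3 mg/kg daily, and the plan budgets for 8 such courses among 66 patients.

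Under Drug reconstitution and administration, "Patients will be monitored for the occurrence of infusion-related toxicity during and after drug infusion". Table 1 marks adverse events at days 3, 7 and 14.

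The Statistical analyses section has only general rules that could apply: "Categorical variables will be summarized by absolute and relative frequencies" and "Categorical variables will be compared with Fisher exact test or chi-square test, as appropriate". The design is called non-comparative. Yet the Objectives include comparing the safety of the three regimens, exploratory comparisons are planned, and the Research Justification expects better tolerability from fewer, higher doses.

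**The concern.** A patient in arm (iii) has about fourteen occasions on which to react, and a patient in arm (i) has one. If the endpoint is tabulated as patients with at least one reaction, which the general rules for categorical data make the likely default, arm (iii) can show a higher frequency only because it has more infusions. A higher reaction risk at 10 mg/kg could then appear as a lower frequency in the high-dose arms.

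Two safety questions are at stake. One is the burden of each regimen over its course. The other is the acute tolerability of a 10 mg/kg infusion against a 3 mg/kg infusion. One undefined frequency cannot be relied on to answer both, and the results are meant to inform a possible phase III trial. Rescue infusions add to the ambiguity, because the endpoint refers to L-AmB without limiting itself to the assigned doses.

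**Working it through.** **Inputs from the protocol.** 33 patients per arm; 1 and 2 infusions in arms (i) and (ii); two weeks at 3 mg/kg in arm (iii); 12% failure and 8 rescue courses in 66 patients. **Assumptions.** Arm (iii) is dosed daily (14 infusions). The risk q per infusion is 2%, 5% or 10%, since the documents give none.

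**1. The plan's own figure.** There is none for this endpoint. The arm size comes from clinical response: 1.645² × 0.88 × 0.12 / 0.10² = 28.57, so 29; then 29 / 0.90 = 32.2, so 33. This reproduces but does not bear on infusion toxicity.

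**2. Planned infusions.** 33 × 1 = 33, 33 × 2 = 66 and 33 × 14 = 462.

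**3. Per-patient frequency, independent infusions.** The formula is 1 − (1 − q)^k with k = 1, 2, 14.

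| q per infusion | Arm (i) | Arm (ii) | Arm (iii) |
|---|---|---|---|
| 2% | 2.0% | 4.0% | 24.6% |
| 5% | 5.0% | 9.8% | 51.2% |
| 10% | 10.0% | 19.0% | 77.1% |

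**4. Allowing for clustering.** Reactions may recur in the same patients. Let the patient's own risk follow a beta distribution with mean q and within-patient correlation ρ, that is a = q(1 − ρ)/ρ and b = (1 − q)(1 − ρ)/ρ. The chance of at least one reaction in k infusions is 1 − B(a, b + k)/B(a, b), where B is the beta function. At q = 5%:

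| ρ | Arm (i) | Arm (ii) | Arm (iii) | Arm (iii) ÷ arm (i) |
|---|---|---|---|---|
| 0 | 5.0% | 9.8% | 51.2% | 10.2 |
| 0.1 | 5.0% | 9.3% | 35.9% | 7.2 |
| 0.3 | 5.0% | 8.3% | 22.4% | 4.5 |
| 0.5 | 5.0% | 7.4% | 15.2% | 3.0 |
| 0.9 | 5.0% | 5.5% | 6.6% | 1.3 |

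The last column is how many times riskier a 10 mg/kg infusion would have to be before arm (i) matched arm (iii) per patient.

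**5. What the planned test would do.** Sum the binomial probabilities of all outcomes at 33 per arm for which Fisher's two-sided p is at most 0.05, arm (i) against arm (iii). With equal 5% risk and independence (5.0% against 51.2%), the test rejects with probability 0.99; at q = 2% it is 0.70. If 10 mg/kg carried four times the risk (20% against 51.2%), arm (i) would still be significantly lower with probability about 0.70. At ρ = 0.3 that masking comparison becomes 20% against 22%, and at ρ = 0.9 it becomes 20% against 7%, where the higher risk shows.

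**6. Rescue.** If 12% of arm (i) had 14 further infusions and these were counted, at q = 5% with independence: 0.88 × 0.05 + 0.12 × (1 − 0.95^15) = 0.044 + 0.064 = 10.8%, against 5.0% for the assigned dose alone.

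**7. What first-infusion data offer.** Every patient has one first study infusion: 10 mg/kg in arms (i) and (ii), 33 + 33 = 66 patients, and 3 mg/kg in arm (iii), 33 patients. With no events, the exact two-sided 95% upper limit is 1 − 0.025^(1/n): 10.6% for n = 33 and 5.4% for n = 66.

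**The case against.** A reader might infer that the plan cannot show whether 10 mg/kg is tolerated. The documents do not support that. Arm (i) has one assigned infusion, so its per-patient and per-infusion frequencies for that dose are the same number. Three reactions in 33 would give 9.1%, exact 95% interval 1.9% to 24.3%: imprecise, but a direct estimate.

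A reader might also infer that the plan prescribes the wrong analysis. It does not: the unit is left open, and a per-infusion frequency is not excluded. The defect is an omission.

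Nor does Table 1 prove that reactions go unlinked to infusions. Its adverse-event marks are scheduled collection points, monitoring around each infusion is required separately, and no case report form is in the documents. Likewise, nothing says rescue infusions will be counted with the assigned ones. Additional L-AmB is an endpoint of its own, so these patients are identifiable.

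The strongest objection is that the trial compares regimens, and fewer infusions is part of the strategy. Per-patient frequency over the course is then a legitimate measure, and a lower figure in arm (i) may be a real benefit. This stands, and is why that measure should be kept. It does not answer the separate question about dose level. It is also right that the 51% belongs to the independence extreme, and that the gap nearly closes under strong clustering.

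The non-comparative label is not a full answer, because the Objectives and the exploratory comparisons both set the arms side by side.

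**Conclusion.** The concern holds in a limited form. The endpoint lacks a unit, and no planned method accounts for infusion counts of 1, 2 and about 14 or for rescue infusions. A per-patient comparison between arms therefore cannot separate dose level from number of infusions. With an equal 5% risk per infusion, arm (i) shows 5% and arm (iii) anywhere from 7% (correlation 0.9) through 22% (0.3) to 51% (independence). The size thus depends heavily on clustering, which the documents do not describe. It also rests on an assumed per-infusion risk and on daily dosing in arm (iii).

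This is a descriptive secondary safety endpoint, and the primary analysis is untouched. The change is still worth making before data are collected, because the link between a reaction and its infusion may not be recoverable later.

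**What to change.** - Define infusion-related toxicity, with its grade threshold and time window around the infusion.
- Record each reaction against its infusion: infusion number, mg/kg given, and whether assigned or rescue. The monitoring already required during and after infusion supplies the information.
- Keep the share of patients with at least one reaction over the assigned course, by arm, labelled as regimen burden.
- Add first-infusion reaction frequency as the dose-level measure: arms (i) and (ii) pooled (n = 66) against arm (iii) (n = 33), with exact intervals. This is a randomized comparison unaffected by infusion count or rescue.
- Note with it that the exclusion criteria permit one polyene dose in the preceding 48 hours, so the first study infusion need not be the first exposure. Show how many patients in each group had one.
- Report reactions to rescue infusions separately.

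The cost is two extra fields on the infusion record and one table, with no added visit or procedure. The short-course arms' apparent tolerability advantage may shrink on the dose-level measure.

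### The only serial fungal-burden endpoint is a yes/no 50% fall in urinary antigen with no assessment day fixed, although concentrations are scheduled at three visits

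*Combined protocol and SAP*

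**What the plan says.** All references are to the combined protocol and SAP.

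- **Secondary endpoints, other measures.** Two candidates are ruled out: "Clearance of blood cultures will not be used as a criterion for mycological response in this study", and "Fungal clearance will also not be used as a criterion for mycological response".
- **Secondary endpoints, antigen.** The marker that remains is judged by "a decrease of at least 50% in *Histoplasma* urinary antigen concentrations", assessed "along the first 2 weeks of therapy as a secondary endpoint, and the association of such reductions with clinical response to antifungal therapy". The association is therefore also built on the threshold. The threshold carries a citation to published consensus response criteria.
- **Study activities, Table 1.** The row "Urine for Histo antigen test" is marked at baseline, day 7 and day 14.
- **Primary endpoint.** Clinical response has a fixed day: "Primary study outcome will be determined at day 14 of the study". The section opens with "Clinical and mycological successes will be the primary outcomes for this study", but mycological success is not defined there or elsewhere.
- **Statistical analyses.** General tests are listed for continuous and for categorical variables. None is assigned to antigen. The trial is described as non-comparative, with exploratory comparisons allowed.

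**The concern.** A concentration measured three times is reduced to one yes/no result. Falls of 49% and 0% count alike, and so do falls of 51% and 99%. Because no day is named, a fall at day 7, at day 14 or at either could qualify, and these are three different endpoints.

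This matters because the plan expects the same clinical response, 88%, in all three arms. Clinical response is then not expected to separate the regimens. With culture and fungal clearance excluded, the rate of antigen fall is the planned measure best placed to show slower activity in one arm, and the objectives do speak of comparing activity.

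The association has a further difficulty. If the fall is read on day 14, it coincides with the response assessment and has no predictive lead. A patient who dies before day 14 cannot meet the response definition and cannot give a day-14 urine, so the small failure group would lose some of its worst outcomes.

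**Working it through.** **1. The plan's own figure.** The documents state no figure for the antigen endpoint. The sample size does reproduce:
- n = (1.645/0.10)² × 0.88 × 0.12 = 28.57, rounded up to 29 per arm
- 29/0.90 = 32.2, rounded up to 33 per arm
- 3 × 33 = 99 in total

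The antigen endpoint plays no part in it.

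**2. Information lost by the cut.** Assume the log antigen change is normal, and let q be the share of patients reaching the 50% fall. The efficiency of the yes/no result relative to the continuous change is φ(z_q)²/[q(1−q)], where φ is the standard normal density and z_q the normal quantile at q. The documents do not give q, so a range is shown.

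| q | z_q | φ(z_q) | Efficiency | Loss | Equivalent n of 29 |
|---|---|---|---|---|---|
| 50% | 0 | 0.399 | 0.64 | 36% | 18.5 |
| 80% | 0.842 | 0.280 | 0.49 | 51% | 14.2 |
| 90% | 1.282 | 0.175 | 0.34 | 66% | 9.9 |

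The smallest loss is 36%, at q = 50%. The loss is exactly half only at q of about 79%. The table covers the cut at one time point. Any further loss from ignoring the other sample depends on a within-patient correlation that is not given.

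**3. Power in one assumed example.** Assumed inputs: SD of the log10 ratio 0.45, mean falls of 0.60 and 0.30 in two arms, two-sided 10%. The 29 per arm comes from the plan.
- A 50% fall is log10(2) = 0.301 on this scale. The shares reaching it are Φ((0.60 − 0.301)/0.45) = 75% and Φ((0.30 − 0.301)/0.45) = 50%.
- Log ratio, t-test: standardised difference 0.30/0.45 = 0.667; non-centrality 0.667 × √(29/2) = 2.54; power 0.806.
- Yes/no, by enumerating all outcomes: uncorrected chi-square 0.626, Fisher 0.504.

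The cut costs 0.806 − 0.626 = 0.18. A further 0.626 − 0.504 = 0.12 comes from Fisher's conservatism, not from the cut.

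**4. The association.** At 88% response, failures number 0.12 × 99 = 11.9, about 12, or 0.12 × 87 = 10.4 among the 3 × 29 evaluable patients. Assume that 80% of 87 responders and 40% of failures reach the fall. Fisher power at two-sided 5% is then:
- 12 failures with urine: 76%
- 9 failures with urine: 70%
- 6 failures with urine: 53%

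The fall rates and the number of failures without a sample are assumptions. The documents give no day-14 death rate.

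**The case against.** The strongest case on the other side has five parts.

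- **Continuous analysis is not excluded.** The statistical section lists t-tests, rank tests and ANOVA, and antigen concentration is a continuous variable. A reader might infer that the concentrations will be discarded; the text does not say so. What stands is that none of these tests is assigned to antigen, while the stated endpoint is the threshold.
- **Same-day reading is not stated.** A reader might infer that the antigen fall is read on the same day as response. The window is the first two weeks and a day-7 sample exists, so the supportable point is that no day is fixed.
- **The size depends on assumptions.** A loss of about half holds only for q near 79%. A reader comparing 81% with Fisher's 50% might also infer that most of the chance to see a difference is gone. The plan allows chi-square too, and expected counts in the example are well above 5, so 63% is the fairer comparison. The loss of half the failures is likewise hypothetical: patients can fail through fever or unresolved symptoms and still give urine.
- **The threshold has a cited source, and the endpoint is secondary** in a trial sized for the precision of clinical response. This limits the consequence. It supports keeping the 50% rate, not making it the only planned antigen result.
- **A continuous model has its own gaps.** Patients may enrol on microscopy, culture, histopathology or PCR, so baseline antigen may be negative. The Rescue therapy section describes additional L-AmB only for arms (i) and (ii), which could affect a day-14 contrast with arm (iii). Both points stand and are taken up in the fix.

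**Conclusion.** The concern holds in a limited form. The only serial fungal-burden endpoint is a threshold with no assessment day, although three concentrations are scheduled. The cut loses about 36% to 66% of the information under a normal log-change model with 50% to 90% of patients reaching the fall. In the assumed example, power drops from about 81% to 63% with chi-square, or 50% with Fisher. The share reaching the fall, the SD and the mean falls are not in the documents.

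The antigen fall may be read on the day of clinical response, because nothing rules that out. With about 12 failures expected, losing a few to early death matters, but how many would be lost is unknown. The association is thin on either measure.

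The documents do not support saying that half the information is lost, that same-day reading is planned, or that continuous analysis is ruled out. The point is worth acting on because the remedy uses samples already scheduled. It does not affect the sample size of 99.

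**What to change.** 1. **Main antigen analysis.** Specify change in log10 concentration from baseline at days 7 and 14, in one repeated-measures model with arm, visit, arm-by-visit and log10 baseline. Restrict it to patients with detectable baseline antigen, and state a rule for later values below detection. Report each arm's mean fall, and exploratory differences from arm (iii), with 90% CI.
2. **Rescue treatment.** Report by arm how many patients had rescue L-AmB before each sample, and treat day 7 as the comparison less affected by it.
3. **Threshold.** Keep the 50% fall as a descriptive rate, read at day 14.
4. **Association.** Use the day-7 antigen ratio against day-14 clinical response in patients alive at day 7, and report earlier deaths alongside.

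The cost is plan wording and some extra analysis; no sample or visit is added. Antigen-negative patients fall outside the model and deaths before day 7 fall outside the association, so both should be counted in the report.

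### The antigen-fall versus clinical-response association has no assigned test and no pooling rule, and the only categorical tests listed ignore randomised arm

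*Combined protocol and SAP*

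**What the plan says.** Secondary endpoints makes the antigen fall a yes/no measure: "we will evaluate the effect of a decrease of at least 50% in *Histoplasma* urinary antigen concentrations [19] along the first 2 weeks of therapy". The same sentence adds the analysis at issue, "the association of such reductions with clinical response to antifungal therapy". Clinical response at day 14 is also yes/no. No test is named for their association, and nothing says whether it is examined in all patients together or within each arm.

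Statistical analyses gives only a general list. For two categorical variables it reads "Categorical variables will be compared with Fisher exact test or chi-square test, as appropriate". No stratified, adjusted or regression method appears anywhere. The comparisons are labelled exploratory ("exploratory comparisons will be performed across subgroups"). A further line says "All p-values will be two-sided", but no significance level is given. The same section states "We expect that the three arms will have the same clinical response".

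Intervention lists three regimens: a single dose of 10 mg/kg; 10 mg/kg followed by 5 mg/kg on day 3; and "L-AmB at 3 mg/kg IV for 2 weeks".

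**The concern.** The question is about patients: does someone whose antigen falls also respond? The data come from three randomised groups with different planned exposure: 10 mg/kg, 10 + 5 = 15 mg/kg, and 3 x 14 = 42 mg/kg if the third regimen is given daily. Regimen could therefore affect both antigen fall and response. A pooled 2x2 table would then mix differences between arms with the link between antigen and response inside an arm, and could create, exaggerate or mask an association. Three separate tables avoid that mixing but contain very few non-responders. The plan does not choose between these two courses, and it lists no method that avoids both problems.

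The protocol rules out blood-culture clearance and fungal clearance as criteria for mycological response, and says the results may serve as a basis for a phase III trial. Whether antigen tracks response within a regimen is therefore a finding that others may use.

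**Working it through.** **Inputs from the plan.** Expected response 88%, failure 12%, 29 evaluable per arm, 10% dropout, 33 per arm, 99 in total. **Assumptions.** Two-sided test level 0.05, and all antigen-fall rates and arm-specific response rates, because the documents give none.

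**1. The plan's own figures.** n = z² p(1−p)/d² = 1.645² x 0.88 x 0.12 / 0.10² = 28.6, so 29. Then 29/0.90 = 32.2, so 33 per arm, and 3 x 33 = 99. These reproduce.

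**2. Non-responders per arm.** 33 x 0.12 = 3.96; 29 x 0.12 = 3.48. So about 3.5 to 4 per within-arm table. The chance of two or fewer is 22% at 33 per arm and 31% at 29. Pooled: 99 x 0.12 = 11.9, or 87 x 0.12 = 10.4.

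**3. What pooling does when there is no association within any arm.** In each arm P(fall and response) = P(fall) x P(response). Average the four cell probabilities over the arms and take the odds ratio.

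Scenario A, fall 60/60/90%, response 80/80/95%:
- Fall and response: (0.480 + 0.480 + 0.855)/3 = 0.605
- Response without fall: 0.850 − 0.605 = 0.245
- Fall without response: 0.700 − 0.605 = 0.095
- Neither: 1 − 0.850 − 0.700 + 0.605 = 0.055
- Pooled odds ratio: (0.605 x 0.055)/(0.245 x 0.095) = 1.43, against a true value of 1

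The same steps give the other odds ratios below. Rejection rates are simulated at 33 per arm. CMH is the asymptotic Cochran-Mantel-Haenszel test stratified by arm.

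| Scenario | Fall by arm (%) | Response by arm (%) | Pooled odds ratio | Pooled Fisher | CMH |
|---|---|---|---|---|---|
| A | 60/60/90 | 80/80/95 | 1.43 | about 8% | about 5% |
| B | 40/50/90 | 65/75/92 | 1.74 | about 18% | about 5% |
| C | 50/50/90 | 92/92/75 | 0.55 | about 10% | about 5% |
| Modest differences | 50/60/70 | 78/83/88 | 1.10 | 3.7% | 4.7% |
| Equal response | 40/60/80 | 88/88/88 | 1.00 | 3.1% | 4.7% |

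The exact CMH test rejects in about 3% to 4% of trials in A to C.

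**4. Masking.** With a within-arm odds ratio of 3, response 88/80/70% and fall 40/60/80%, the pooled odds ratio drops to 1.80. Power is 18% for pooled Fisher and 49% for CMH. If response is 88% everywhere and only fall differs (40/60/80%), a within-arm odds ratio of 4 becomes 3.37 when pooled, a mild attenuation.

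**5. Power when arms do not differ.** Assume a strong association: fall in 80% of responders and 30% of non-responders, an odds ratio of (0.8/0.2)/(0.3/0.7) = 9.3, with 88% response in every arm.
- Fisher in one arm of 33: about 40% (35% at 29)
- Fisher pooled over 99: about 91%
- CMH over 99: about 92% asymptotic, about 90% exact

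**The case against.** The strongest reply is that the plan has not chosen a faulty test. A reader might infer that it commits to a pooled, unstratified Fisher or chi-square test of this association. The documents do not support that: the sentence on categorical variables is general, and the association is assigned neither a test nor a pooling rule. Nor do they say that it will be tested arm by arm. The gap is an analysis left open, with only arm-blind tests on the list.

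The second reply is that a false association needs arms that differ in both antigen fall and response, whereas the plan expects equal response. That is correct, and under equal response the pooled odds ratio is 1.00. The 18% figure needs a 27-point gap in response and a 50-point gap in antigen fall. But equal response is an expectation about something the trial sets out to examine: Objectives speaks of comparing the regimens' activity, and Research Justification treats the activity of the high-dose strategy in this disease as an open question. The analysis need not depend on that expectation.

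The third reply concerns power. Setting about 40% in one arm against about 92% stratified might suggest that stratifying more than doubles power. Most of that contrast is 33 patients against 99; pooled Fisher on the same 99 already has about 91%.

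Two further inferences fail. Scenario C does not show a reversed direction, because the true within-arm association there is null. And stratifying does not guarantee that all 99 patients contribute. Patients may enter on microscopy, culture, histopathology or PCR without a positive urine antigen, and a 50% fall needs both a measurable baseline and a follow-up sample.

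**Conclusion.** The point holds as a minor one. The association is planned without a test or a pooling rule, and none of the listed categorical methods accounts for arm. If arms differ substantially in both variables, pooling distorts the estimate (odds ratio 0.55 to 1.74 where the truth is 1) and raises Fisher false positives to about 8% to 18%. If response is equal across arms there is no false association, and for modest differences the distortion is small. Arm-by-arm testing has too few non-responders to be useful. These sizes rest on assumed arm-specific rates and an assumed 0.05 level; only the 88% response and the arm sizes come from the plan. The analysis is secondary and exploratory in a trial described as non-comparative, so no primary estimate and no part of the sample size changes.

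**What to change.** Add to Statistical analyses that the association between an antigen fall of at least 50% and day-14 clinical response is estimated in one analysis stratified by randomised arm. It should report the Mantel-Haenszel odds ratio with a confidence interval and a Cochran-Mantel-Haenszel test, exact if counts are sparse. State that the analysis set is patients with a measurable baseline antigen and a follow-up sample, and give their number by arm. Show the three within-arm 2x2 tables descriptively, without separate tests.

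This costs one or two sentences and a standard procedure, with no new patients, visits or samples. The downside is that the exact version is slightly conservative: about 90% power against 91% for pooled Fisher when the arms are alike.
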